#### **Sample size**

The "single stage procedure" proposed by Fleming was used to estimate the sample size for this type of trial. For  $P_0=10\%$  and  $P_1=30\%$  with an alpha error of 5% and a beta of 80%, 18 patients need to be included in order to prove the study's hypothesis. After adjusting this number by a percentage of loss of 30%, which is observed in daily practice, 24 patients will be included in the study.

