## OUTCOMES

### Primary Outcome

Proportion of patients with clinical improvement of premature ejaculation, defined as a tripling of the baseline time (without treatment), as measured by the IELT (intravaginal ejaculation latency time) during the therapy and three months after completion.

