### Data Analysis Plan

A descriptive analysis will be performed of the sociodemographic and clinical characteristics of the research subjects. For the categorical variables, absolute and relative frequencies will be estimated. For the numerical variables, central tendency and dispersion measurements will be estimated.

To evaluate the efficacy of this new therapy, the proportion of patients whose illness improves will be estimated and compared with the expected proportion proposed by the hypothesis (30%). Improvement is defined as the tripling of the baseline (without treatment) intravaginal latency time.

The safety will be evaluated by estimating the incidence of adverse events experienced by the patients during the study. These will be classified by the degree of severity according to WHO criteria.

The analyses will be performed with Stata 14.

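### With 18 patients, no responder cut-off gives both 5% alpha and 80% power for 10% versus 30%; keeping one-sided alpha within 5% leaves exact power of 67%

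*Combined protocol and SAP*

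**What the plan says.** The Sample size section names Fleming's single-stage procedure, sets P0 = 10% and P1 = 30%, and states that "with an alpha error of 5% and a beta of 80%, 18 patients need to be included". It then allows for 30% loss and concludes that "24 patients will be included in the study". It does not say whether alpha is one- or two-sided, whether the test is exact or approximate, or how many responders would count as success.

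The endpoint is binary. The Primary Outcome section defines it as "Proportion of patients with clinical improvement of premature ejaculation, defined as a tripling of the baseline time (without treatment"), measured by IELT.

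The Data Analysis Plan names no test. It says that the proportion improved will be estimated and "compared with the expected proportion proposed by the hypothesis (30"%). That value is P1, the alternative, and not the P0 of 10% used for sizing.

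**The concern.** A single-stage, single-arm design amounts to a sample size and a responder cut-off, and the pair fixes both error rates. Here only the sample size is given. The number of responders is a whole number, so with 18 patients only a few pairs of alpha and power are possible, and the stated pair may not be among them.

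The stated error rates are the only statistical justification for the sample size of this uncontrolled phase II study, which is meant to support later comparative trials. If they cannot be reached, the chance of missing a true 30% response rate is larger than the one in five implied. If no cut-off is fixed, 4 responders out of 18 could be called a success or a failure after the fact.

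**Working it through.** **Inputs** (Sample size section): P0 = 0.10, P1 = 0.30, alpha 0.05, power 0.80, n = 18 evaluable, 24 enrolled, 30% loss. Assumptions: one-sided alpha, the reading kinder to the plan; and the 80% printed as beta means power. A literal beta of 80% would mean 20% power, which is not a sensible target.

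**1. The plan's own figure.** Large-sample formula, one-sided 5%, power 80%:

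n = [(z_alpha·√(P0(1−P0)) + z_power·√(P1(1−P1))) / (P1−P0)]²
= [(1.6449 × 0.3000 + 0.8416 × 0.4583) / 0.20]² = 19.32, so 20.

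The same approximation at n = 18 gives power Φ[(√18 × 0.20 − 1.6449 × 0.3000) / 0.4583] = Φ(0.775) = 78.1%. So 18 is close to the approximate answer but slightly below it.

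**2. Exact error rates at n = 18.** With cut-off r, alpha = P(X ≥ r | 0.10) and power = P(X ≥ r | 0.30), X binomial. For r = 5:

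- alpha = 1 − (0.1501 + 0.3002 + 0.2835 + 0.1680 + 0.0700) = 0.0282
- power = 1 − (0.0016 + 0.0126 + 0.0458 + 0.1046 + 0.1681) = 0.6673

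| Cut-off of 18 | Exact one-sided alpha | Exact power |
|---|---|---|
| ≥4 | 9.8% | 83.5% |
| ≥5 | 2.8% | 66.7% |
| ≥6 | 0.6% | 46.6% |

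No row has alpha at or below 5% together with power at or above 80%.

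**3. Other evaluable numbers.** A 30% loss from 24 leaves 24 × 0.70 = 16.8, about 17. Taking the smallest cut-off with exact one-sided alpha ≤5%:

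| n | Cut-off | Alpha | Power |
|---|---|---|---|
| 17 | ≥5 | 2.2% | 61.1% |
| 18 | ≥5 | 2.8% | 66.7% |
| 19 | ≥5 | 3.5% | 71.8% |
| 20 | ≥5 | 4.3% | 76.3% |
| 21 | ≥6 | 1.4% | 63.7% |
| 22 | ≥6 | 1.8% | 68.7% |
| 23 | ≥6 | 2.3% | 73.1% |
| 24 | ≥6 | 2.8% | 77.1% |
| 25 | ≥6 | 3.3% | 80.7% |

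The first number to reach 80% is 25.

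**4. Two-sided reading.** With equal tails (upper tail ≤2.5%) the cut-off at 18 is ≥6, power 46.6%, and the first adequate n is 29 (≥7; upper tail 2.2%, power 81.2%). An exact two-sided test that orders outcomes by their probability gives p = 0.028 for 5 of 18, so its cut-off is ≥5 and its power is again 66.7%.

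**5. The comparison with 30%.** If it were a one-sided 5% superiority test against 30%, success at n = 18 would need ≥10 responders, and the chance of that at a true rate of 30% is 2.1%. It therefore cannot be the test that was sized.

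**The case against.** The strongest defence is that 18 is a large-sample figure and not a blunder. The standard approximation gives 19.3, and approximate power at 18 is 78.1%. A variant using two-sided 5% and only the P0 variance gives (1.960 + 0.842)² × 0.09 / 0.20² = 17.7, which rounds up to exactly 18. Under a one-sided normal-approximation test, 4 of 18 is significant: z = (0.222 − 0.100) / √(0.09/18) = 1.73, above 1.645. That rule has 83.5% power, so the plan meets its targets nominally.

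This may explain where 18 came from, though the protocol does not say which formula was used. It does not make the stated rates true: the rule that declares success at 4 of 18 has a real alpha of 9.8%, about twice what is stated. The impossibility is a statement about exact error rates, which are the ones that matter at this sample size.

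Two qualifications stand. The 46.6% and 29 in the two-sided reading belong to the equal-tailed convention only. And 61.1% is not a secure floor: if 16 patients were evaluable, power would be 55.0%.

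**Conclusion.** The concern holds. Under exact binomial error rates, 18 patients cannot give 5% alpha and 80% power for 10% versus 30% at any cut-off. With one-sided alpha within 5%, power is 66.7%, a one-in-three chance of missing a true 30% rate. It stays between 61.1% and 77.1% for every evaluable number from 17 to 24. Keeping 80% power at 18 means accepting an alpha of 9.8%.

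This rests on two readings: one-sided testing, and 80% meaning power. Neither rescues the design, since two-sided testing gives 66.7% or less. The Data Analysis Plan leaves the gap open by naming P1 as the comparison value and giving no test. The trial can proceed, but its stated error rates should be corrected and its decision rule written down.

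**What to change.** Keep the enrolment of 24 and state the rule and its real properties. In the Sample size section, write for example:

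> One-sided exact binomial test against P0 = 10%. Success is the smallest responder count with exact one-sided alpha ≤5%: at least 5 with 17 to 20 evaluable patients, at least 6 with 21 to 24; the same rule applies to any other number. With 18 evaluable: at least 5, alpha 2.8%, power 67% at P1 = 30% (61% at 17, 77% at 24).

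Replace the beta figure with the attained power. In the Data Analysis Plan, replace the comparison with 30% by this same test against 10%, and report the proportion with an exact confidence interval.

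The alternative is to declare a one-sided alpha of 10% in both sections. Examples: at least 4 of 17 (alpha 8.3%, power 79.8%), at least 4 of 18 (9.8%, 83.5%), at least 5 of 24 (8.5%, 88.9%). With 19 or 20 evaluable, a cut-off of 4 would exceed 10% (11.5% and 13.3%), so 5 is needed and power is 71.8% or 76.3%; these should be stated too.

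Either way, fix the choice before outcome data are analysed. No patients, visits or procedures change. The cost is a written decision rule in two sections and a less favourable stated power or alpha. Keeping both 5% and 80% would instead need 25 evaluable patients, or 25 / 0.70 = 35.7, so 36 enrolled, at the plan's own loss rate.

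### The sample-size statement labels 80% as beta where power was almost certainly meant, and the power that 18 evaluable patients give is not stated

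*Combined protocol and SAP*

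**What the plan says.** The combined protocol and SAP has one sample-size paragraph, under Materials and Methods, Sample size. It names the method (the single-stage procedure "proposed by Fleming was used to estimate the sample size for this type of trial"), sets P0 = 10% and P1 = 30%, and continues "with an alpha error of 5% and a beta of 80%, 18 patients need to be included". The 18 are then raised for an expected loss of 30%, so that "24 patients will be included in the study". The rates refer to the primary outcome, the proportion of men whose intravaginal latency time at least triples from baseline.

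The paragraph does not say whether alpha is one- or two-sided, and it gives no number of responders at which the null would be rejected. The Data Analysis Plan supplies neither. No other section states a power or a type II error.

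**The concern.** Alpha and beta are printed side by side as a pair of error rates, so a reader will take beta in its standard sense: the probability of not rejecting the null when the true responder rate is 30%. At 80%, the plan says that a therapy with the hoped-for effect would be missed four times in five. That does not agree with the sample size in the same sentence.

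This is the only place where the planned false-negative rate can be found. A reader who has to interpret a non-significant result, or who tries to reproduce the calculation, is given a wrong value. Replacing it with 80% power and stopping there would leave a second inaccuracy, because 18 patients do not deliver exactly 80% under a 5% test.

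**Working it through.** **Inputs from the Sample size section:** P0 = 0.10, P1 = 0.30, alpha = 0.05, stated n = 18, loss 30%, enrolled n = 24.

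**Assumptions:** alpha is taken as one-sided, as is usual for a single-arm, single-stage test; two-sided results are also given. The test is taken to be against P0 = 10%, as in the Sample size section.

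**1. Can the plan's 18 be reproduced?**

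Normal-approximation formula for the single-stage design:

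n = [(z(1−alpha)·√(P0(1−P0)) + z(power)·√(P1(1−P1))) / (P1 − P0)]²

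Here √(0.1·0.9) = 0.3 and √(0.3·0.7) = 0.4583.

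- 80% read as power, one-sided: [(1.645·0.3 + 0.842·0.4583)/0.2]² = 19.3, so 20 patients.
- 80% read as power, two-sided: 23.7, so 24 patients.
- 80% read as power, two-sided, using the null variance only: (1.960 + 0.842)²·0.09/0.04 = 17.7, so 18 patients.

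Reading 80% as power therefore gives sizes around 18. The plan does not say which variant was used. The step from 18 to 24 is 18 × 1.3 = 23.4, rounded up, and does not involve beta.

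**2. What does the printed beta imply?**

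Beta = 80% is power = 20%, for which z(power) = −0.842.

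- One-sided formula: [(1.645·0.3 − 0.842·0.4583)/0.2]² = 0.29. Two-sided: 1.02. A large-sample formula means little at this size, so the exact result is the one to use.
- Exact binomial, one-sided: with n = 3 and rejection at 2 or more responders, alpha = 3·0.1²·0.9 + 0.1³ = 0.028 and power = 3·0.3²·0.7 + 0.3³ = 0.216. With n = 2, power is only 0.3² = 0.09. So 3 patients suffice.
- Continuity-corrected and arcsine versions, one- and two-sided, give 2.4 to 4.7.

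None of these is near 18.

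**3. What power do 18 evaluable patients give?**

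Normal approximation: power = Φ((0.2·√18 − z·0.3)/0.4583).

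- One-sided, z = 1.645: Φ(0.775) = 78.1%.
- Two-sided, z = 1.960: 71.5%.

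Exact binomial at n = 18:

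| Reject at | Alpha (rate 10%) | Power (rate 30%) | Beta |
|---|---|---|---|
| 4 or more | 0.098 | 83.5% | 16.5% |
| 5 or more | 0.028 | 66.7% | 33.3% |
| 6 or more | 0.006 | 46.6% | 53.4% |

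The normal boundary is 18·0.1 + 1.645·√(18·0.1·0.9) = 3.89. Rejecting at the next whole number gives a cut-off of 4; rounding to the nearest whole number and adding one gives 5. Only 5 keeps exact alpha within a one-sided 5%. If the 5% were two-sided, with 2.5% in the upper tail, the cut-off would be 6. No cut-off at n = 18 gives both alpha of at most 5% and power of at least 80%.

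**The case against.** The best defence is that this is a slip any statistician would see through. The figure of 80% stands beside P0, P1, alpha and n, and these point to power. Entering 0.80 as a type II error in software returns a handful of patients, so the mistake shows at once. The figure is not used again in the outcomes or the analysis plan, and correcting it changes no patient's participation. All of this stands, and it is why the point is minor.

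The defence does not remove the error. The statement is wrong as printed and nothing elsewhere in the document corrects it.

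Some stronger readings are tempting, and the documents do not support them:

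- A reader might infer that the trial was planned with 20% power, so that a negative result would say nothing. The stated 18 patients contradict this: under every rule in the table power is well above 20%.
- A reader might infer that the false-negative rate is overstated fourfold. The ratio 80/20 compares the printed value with an inferred target. Against the error at 18 patients it is about 2.4 (80/33.3) for a cut-off of 5, or 3.7 (80/21.9) by the one-sided normal approximation.
- A reader might infer that more patients must be enrolled. The mislabelling does not show that. The shortfall from 80% can be disclosed, and whether to enlarge the trial is a separate decision.

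**Conclusion.** The point holds as a labelling error with a gap behind it. A beta of 80% cannot yield 18 patients: about 3 would be enough by the exact one-sided calculation. A power of 80% gives 19.3 by the one-sided formula. That power was meant is an inference, since no other section states it, but it is the only one of the two readings that comes near the stated size.

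The power at 18 evaluable patients depends on choices the plan leaves open. It is about 78% by the one-sided normal approximation and 66.7% exactly with a cut-off of 5. A cut-off of 4 raises it to 83.5%, but with alpha of 0.098. These figures assume a test against 10% and a true rate of 30%.

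Severity is minor: neither conduct nor enrolment changes. What any record outside the document says about power cannot be judged from it.

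**What to change.** In the Sample size section:

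1. Replace the beta of 80% with a target power of 80% (beta 20%).
2. State whether alpha is one- or two-sided, and the number of responders out of 18 at which the null is rejected.
3. Give the power and alpha that follow from that rule. For a one-sided exact test this could read: with 18 evaluable patients the null is rejected at 5 or more responders, with exact alpha 0.028 and power 66.7% at a true rate of 30%. If the normal approximation is kept, say so and give about 78%. If a cut-off of 4 is chosen, report alpha as 0.098, not 5%.

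The cost is two or three sentences in one section, with no change to enrolment or conduct. The downside is that, unless the cut-off of 4 is chosen, the document will show a power below 80%.

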## **Data Collection and Processing Techniques and Procedures**

The patients are admitted to the clinic where they receive a medical evaluation in which they are diagnosed as patients with primary PE. Once this occurs, they are invited to participate in the study by their own voluntary choice. If the patient is interested in participating, the informed consent process is conducted and the corresponding document is signed. Then, an informational email is sent to the telephone center staff responsible for investigations, so that the information required from the patient is inputted into the corresponding database for the purpose of following-up on all of the therapy and follow-up appointments.

Prior to receiving therapy, the patient will perform a two-week process in which he will measure the intravaginal latency time with a digital timer or stopwatch APP and record it on the in-home chart. This has two objectives: first, the patient adapts to the way in which he will measure this time when having sexual relations during the study; second, to have a more precise reference point for the initial IELT, which will be used as a baseline to demonstrate changes during the study protocol.

The therapy will be conducted as follows: Three (3) sessions per week for twelve (12) consecutive weeks, with a duration of 30 minutes each, with the application of 20 Hertz with a pulse amplitude of 200 MI sec. in each session. The intensity will be applied individually for each patient depending on the tolerance of the individual. In each session, it is normal to have plantar flexion of the foot and flexion of the first toe, and after the session and particularly during the first sessions there is the possibility of muscle pain, which should be tolerable. Appendices 3 and 4 provide a more detailed description of the scheme and procedure.

During the study, each patient will have an in-home chart which he must fill out after each sexual encounter and bring to each appointment. The patients will be given strict telephone follow-up calls aimed at their keeping their monthly follow-up appointments, or if not possible due to lack of time a virtual appointment will be conducted by the physician using skype or by telephone.

It is essential that each patient who is admitted into the study complies with the scheduled electrostimulation sessions. If one of the protocols is broken, the patient will be treated as a loss to follow-up since his information could be incorrect.

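### Enrolling 24 patients does not allow for the stated 30% loss: about 17 would remain, against the 18 the plan requires

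*Combined protocol and SAP*

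**What the plan says.** The Sample size section of the combined protocol and SAP uses Fleming's single-stage procedure with P0 = 10%, P1 = 30%, an alpha of 5% and a beta printed as 80%, which I read as power of 80%. It concludes that "18 patients need to be included in order to prove the" hypothesis, and continues: "After adjusting this number by a percentage of loss of 30%, which is observed in daily practice, 24 patients will be included". It prints no formula for the adjustment.

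The section on data collection and processing procedures widens what counts as a loss: "If one of the protocols is broken, the patient will be treated as a loss to follow-up since his information could be incorrect".

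The second section headed Sample describes consecutive recruitment and does not mention replacing patients who are lost. The Data Analysis Plan compares the proportion improved with 30%, but it defines no analysis set and does not say how lost patients are counted.

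**The concern.** The purpose of the adjustment is that the required 18 should still be there after the expected losses. A loss rate seen in daily practice is most naturally the share of patients who start and then drop out, so it applies to the number enrolled. Read that way, the requirement of 18, the loss of 30% and the enrolment of 24 cannot all hold.

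At stake is whether the sample-size statement can be relied on. As written, it tells readers and the ethics committee that a 30% loss has been provided for. At that rate the trial should expect to finish below its own requirement.

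**Working it through.** **Inputs.** All come from the Sample size section: 18 required, 30% loss, 24 enrolled, P0 = 10%, P1 = 30%, alpha 5%.

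**Reproducing the plan's figure.** Adding 30% to the base gives 18 × 1.30 = 23.4, rounded up to 24. This matches the stated enrolment. Because no formula is printed, it is an inference that 24 was obtained this way.

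**Testing it against the stated loss.**

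- Expected to remain: 24 × (1 − 0.30) = 16.8, about 17.
- Shortfall: 18 − 16.8 = 1.2 patients.
- Largest loss that leaves 18 of 24: 1 − 18/24 = 25%.
- Enrolment needed to keep 18: 18/(1 − 0.30) = 25.7, so 26.
- Check: 26 × 0.70 = 18.2, which is at least 18.

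**Chance of reaching 18.** If each patient is lost independently with probability 0.30, the number remaining is binomial. The probability that at least 18 remain is 38.9% with 24 enrolled and 62.7% with 26. At its stated loss rate, the plan is more likely than not to miss its requirement.

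**Effect on power.** The plan gives no responder cut-off and no sidedness, so a test has to be assumed. I use a one-sided exact binomial test against 10%, with power calculated at 30%.

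| Patients remaining | Responders needed | Actual alpha | Power |
|---|---|---|---|
| 17 | 5 or more | 2.2% | 61.1% |
| 18 | 5 or more | 2.8% | 66.7% |
| 17 | 4 or more | 8.3% | 79.8% |
| 18 | 4 or more | 9.8% | 83.5% |

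Five is the smallest cut-off that keeps alpha at or below 5% at both sizes. With it, going from 18 to 17 costs 66.7 − 61.1 = 5.6 points. The cut-off of four exceeds the stated 5% alpha and is shown only for its sensitivity: 83.5 − 79.8 = 3.7 points.

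Next, average over a random 30% loss, choosing at each number remaining the smallest cut-off with alpha of at most 5%. Power is then 61.6% with 24 enrolled and 65.2% with 26, a difference of 3.6 points.

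**Where the rest of the power gap lies.** With exactly 18 patients and no further loss, power is 66.7% under this test. Most of the distance from 80% therefore comes from the base of 18 and not from the loss adjustment.

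**The case against.** The strongest defence is that 24 is not a slip. The text adjusts the base number by 30%, and 18 × 1.30 does round up to 24, so the disagreement is about the method of inflation. This explains the figure but does not rescue it. A 30% mark-up on 18 covers a loss of 1 − 18/23.4 = 23% before rounding and 25% after. It never covers 30% of those enrolled.

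A second objection is that the shortfall exists only if lost patients leave the denominator, and the plan does not say that they do. That is fair, and the conclusion rests on this assumption. However, if losses were kept in the analysis as non-responders, the number analysed would not fall and there would be no reason to inflate 18. The adjustment itself implies that lost patients drop out. So does the reason given for reclassifying protocol-breakers, which is that their information may be incorrect.

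A third is that loss in the trial may be lower than in daily practice, because men who would have difficulty attending are excluded and telephone follow-up is planned. It could also be higher, because broken protocols count as loss. The documents do not settle the direction, and 30% is the rate the plan chose.

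The objection that the effect is small stands in full. It limits how much weight the point deserves, but it does not make the sentence correct.

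**Conclusion.** The concern holds: the Sample size statement is wrong as written. Twenty-four patients allow for a 25% loss, not 30%, and at 30% about 17 are expected to remain against the 18 required. In enrolment terms the discrepancy is two patients, 26 against 24, and nothing in it biases the estimated response proportion.

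Two readings support this conclusion: the 30% is a share of those enrolled, and lost patients are left out of the analysis. The arithmetic needs no further assumption. The power differences depend in addition on the assumed one-sided exact test. The point should be corrected, but it is minor beside the separate question of whether 18 is an adequate base.

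**What to change.** If enrolment stays at 24, replace the adjustment sentence with wording such as: 24 patients allow for a 25% loss, leaving 18 evaluable; at a 30% loss about 17 are expected to be evaluable. This costs one sentence and no patients. It corrects the statement but does not remove the shortfall at 30%. No power figure is needed there; if one is added, give the test, sidedness, responder cut-off and actual alpha with it.

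If the sponsor prefers to keep both the 30% loss and 18 evaluable patients, state an enrolment of 26, at a cost of two more patients.

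If the base of 18 is itself revised, divide the new base by 0.70 so that the same error is not carried onto a larger number.
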